11. MEASUREMENT OF EFFECT

Although response is not the primary endpoint of this trial, participants with measurable disease will be assessed by standard criteria. For the purposes of this study, participants should be re-evaluated every 12 weeks. In addition to a baseline scan, confirmatory scans will also be obtained 4 weeks following initial documentation of an objective response.

11.1 Antitumor Effect – Solid Tumors

For the purposes of this study, participants should be re-evaluated for response every 8 weeks. In addition to a baseline scan, confirmatory scans should also be obtained 4 weeks following initial documentation of objective response.

Response and progression will be evaluated in this study using the new international criteria proposed by the Response Evaluation Criteria in Solid Tumors (RECIST) guideline (version 1.1) [Eur J Ca 45:228-247, 2009]. Changes in the largest diameter (unidimensional measurement) of the tumor lesions and the shortest diameter in the case of malignant lymph nodes are used in the RECIST criteria.

11.1.1 Definitions

Evaluable for Target Disease response. Only those participants who have measurable disease present at baseline, have received at least one cycle of therapy, and have had their disease re-evaluated will be considered evaluable for target disease response. These participants will have their response classified according to the definitions stated below. (Note: Participants who exhibit objective disease progression prior to the end of cycle 1 will also be considered evaluable.)

Evaluable Non-Target Disease Response. Participants who have lesions present at baseline that are evaluable but do not meet the definitions of measurable disease, have received at least one cycle of therapy, and have had their disease re-evaluated will be considered evaluable for non-target disease. The response assessment is based on the presence, absence, or unequivocal progression of the lesions.

11.1.2 Disease Parameters

Measurable disease. Measurable lesions are defined as those that can be accurately measured in at least one dimension (longest diameter to be recorded) as ≥ 20 mm by chest x-ray or ≥ 10 mm with CT scan, MRI, or calipers by clinical exam. All tumor measurements must be recorded in millimeters (or decimal fractions of centimeters).

Note: Tumor lesions that are situated in a previously irradiated area might or might not be considered measurable

Malignant lymph nodes. To be considered pathologically enlarged and measurable, a lymph node must be ≥ 15 mm in short axis when assessed by CT scan (CT scan slice thickness recommended to be no greater than 5 mm). At baseline and in follow-up, only

the short axis will be measured and followed.

Non-measurable disease. All other lesions (or sites of disease), including small lesions (longest diameter <10 mm or pathological lymph nodes with ≥ 10 to <15 mm short axis), are considered non-measurable disease. Bone lesions, leptomeningeal disease, ascites, pleural/pericardial effusions, lymphangitis cutis/pulmonitis, inflammatory breast disease, abdominal masses (not followed by CT or MRI), and cystic lesions are all considered non-measurable.

Note: Cystic lesions that meet the criteria for radiographically defined simple cysts should not be considered as malignant lesions (neither measurable nor non-measurable) since they are, by definition, simple cysts.

'Cystic lesions' thought to represent cystic metastases can be considered as measurable lesions, if they meet the definition of measurability described above. However, if non-cystic lesions are present in the same participant, these are preferred for selection as target lesions.

Target lesions. All measurable lesions up to a maximum of 2 lesions per organ and 5 lesions in total, representative of all involved organs, should be identified as **target lesions** and recorded and measured at baseline. Target lesions should be selected on the basis of their size (lesions with the longest diameter), be representative of all involved organs, but in addition should be those that lend themselves to reproducible repeated measurements. It may be the case that, on occasion, the largest lesion does not lend itself to reproducible measurement in which circumstance the next largest lesion which can be measured reproducibly should be selected. A sum of the diameters (longest for non-nodal lesions, short axis for nodal lesions) for all target lesions will be calculated and reported as the baseline sum diameters. If lymph nodes are to be included in the sum, then only the short axis is added into the sum. The baseline sum diameters will be used as reference to further characterize any objective tumor regression in the measurable dimension of the disease.

Non-target lesions. All other lesions (or sites of disease) including any measurable lesions over and above the 5 target lesions should be identified as **non-target lesions** and should also be recorded at baseline. Measurements of these lesions are not required, but the presence, absence, or in rare cases unequivocal progression of each should be noted throughout follow up.

11.1.3 Methods for Evaluation of Disease

All measurements should be taken and recorded in metric notation using a ruler, calipers, or a digital measurement tool. All baseline evaluations should be performed as closely as possible to the beginning of treatment and never more than 4 weeks before the beginning of the treatment.

The same method of assessment and the same technique should be used to characterize

each identified and reported lesion at baseline and during follow-up. Imaging-based evaluation is preferred to evaluation by clinical examination unless the lesion(s) being followed cannot be imaged but are assessable by clinical exam.

Clinical lesions. Clinical lesions will only be considered measurable when they are superficial (*e.g.*, skin nodules and palpable lymph nodes) and ≥ 10 mm in diameter as assessed using calipers (*e.g.*, skin nodules). In the case of skin lesions, documentation by color photography, including a ruler to estimate the size of the lesion, is recommended.

Chest x-ray. Lesions on chest x-ray are acceptable as measurable lesions when they are clearly defined and surrounded by aerated lung; however, CT is preferable.

Conventional CT and MRI. This guideline has defined measurability of lesions on CT scan based on the assumption that CT thickness is 5mm or less. If CT scans have slice thickness greater than 5 mm, the minimum size of a measurable lesion should be twice the slice thickness. MRI is also acceptable in certain situations (*e.g.* for body scans).

Use of MRI remains a complex issue. MRI has excellent contrast, spatial, and temporal resolution; however, there are many image acquisition variables involved in MRI, which greatly impact image quality, lesion conspicuity, and measurement. Furthermore, the availability of MRI is variable globally. As with CT, if an MRI is performed, the technical specifications of the scanning sequences used should be optimized for the evaluation of the type and site of disease. Furthermore, as with CT, the modality used at follow-up should be the same as was used at baseline and the lesions should be measured/assessed on the same pulse sequence. It is beyond the scope of the RECIST guidelines to prescribe specific MRI pulse sequence parameters for all scanners, body parts, and diseases. Ideally, the same type of scanner should be used and the image acquisition protocol should be followed as closely as possible to prior scans. Body scans should be performed with breath-hold scanning techniques, if possible.

FDG-PET. While FDG-PET response assessments need additional study, it is sometimes reasonable to incorporate the use of FDG-PET scanning to complement CT scanning in assessment of progression (particularly possible 'new' disease). New lesions on the basis of FDG-PET imaging can be identified according to the following algorithm:

- (a) Negative FDG-PET at baseline, with a positive FDG-PET at follow-up is a sign of PD based on a new lesion.
- (b) No FDG-PET at baseline and a positive FDG-PET at follow-up: If the positive FDG-PET at follow-up corresponds to a new site of disease confirmed by CT, this is PD. If the positive FDG-PET at follow-up is not confirmed as a new site of disease on CT, additional follow-up CT scans are needed to determine if there is truly progression occurring at that site (if so, the date of PD will be the date of the initial abnormal FDG-PET scan). If the positive FDG-PET at follow-up corresponds to a pre-existing site of disease on CT that is not progressing on the basis of the anatomic images, this is not PD.

(c) FDG-PET may be used to upgrade a response to a CR in a manner similar to a biopsy in cases where a residual radiographic abnormality is thought to represent fibrosis or scarring. The use of FDG-PET in this circumstance should be prospectively described in the protocol and supported by disease-specific medical literature for the indication. However, it must be acknowledged that both approaches may lead to false positive CR due to limitations of FDG-PET and biopsy resolution/sensitivity.

Note: A 'positive' FDG-PET scan lesion means one which is FDG avid with an uptake greater than twice that of the surrounding tissue on the attenuation corrected image.

PET-CT. At present, the low dose or attenuation correction CT portion of a combined PET-CT is not always of optimal diagnostic CT quality for use with RECIST measurements. However, if the site can document that the CT performed as part of a PET-CT is of identical diagnostic quality to a diagnostic CT (with IV and oral contrast), then the CT portion of the PET-CT can be used for RECIST measurements and can be used interchangeably with conventional CT in accurately measuring cancer lesions over time. Note, however, that the PET portion of the CT introduces additional data which may bias an investigator if it is not routinely or serially performed.

11.1.4 Response Criteria

11.1.4.1 Evaluation of Target Lesions

Complete Response (CR): Disappearance of all target lesions. Any pathological lymph nodes (whether target or non-target) must have reduction in short axis to <10 mm.

Partial Response (PR): At least a 30% decrease in the sum of the diameters of target lesions, taking as reference the baseline sum diameters.

Progressive Disease (PD): At least a 20% increase in the sum of the diameters of target lesions, taking as reference the smallest sum on study (this includes the baseline sum if that is the smallest on study). In addition to the relative increase of 20%, the sum must also demonstrate an absolute increase of at least 5 mm. (Note: the appearance of one or more new lesions is also considered progressions).

Stable Disease (SD): Neither sufficient shrinkage to qualify for PR nor sufficient increase to qualify for PD, taking as reference the smallest sum diameters while on study.

11.1.4.2 Evaluation of Non-Target Lesions

Complete Response (CR): Disappearance of all non-target lesions and normalization of tumor marker level. All lymph nodes must be non-pathological in size (<10 mm short axis).

Note: If tumor markers are initially above the upper normal limit, they must normalize for a patient to be considered in complete clinical response.

Non-CR/Non-PD: Persistence of one or more non-target lesion(s) and/or maintenance of tumor marker level above the normal limits.

Progressive Disease (PD): Appearance of one or more new lesions and/or *unequivocal progression* of existing non-target lesions. *Unequivocal progression* should not normally trump target lesion status. It must be representative of overall disease status change, not a single lesion increase.

Although a clear progression of “non-target” lesions only is exceptional, the opinion of the treating physician should prevail in such circumstances, and the progression status should be confirmed at a later time by the review panel (or Principal Investigator).

11.1.4.3 Evaluation of New Lesions

The finding of a new lesion should be unequivocal (i.e. not due to difference in scanning technique, imaging modality, or findings thought to represent something other than tumor (for example, some ‘new’ bone lesions may be simply healing or flare of pre-existing lesions). However, a lesion identified on a follow-up scan in an anatomical location that was not scanned at baseline is considered new and will indicate PD. If a new lesion is equivocal (because of small size etc.), follow-up evaluation will clarify if it truly represents new disease and if PD is confirmed, progression should be declared using the date of the initial scan on which the lesion was discovered.

11.1.4.4 Evaluation of Best Overall Response

The best overall response is the best response recorded from the start of the treatment until disease progression/recurrence (taking as reference for progressive disease the smallest measurements recorded since the treatment started). The patient's best response assignment will depend on the achievement of both measurement and confirmation criteria.

For Participants with Measurable Disease (i.e., Target Disease)

Target Lesions	Non-Target Lesions	New Lesions	Overall Response	Best Overall Response when Confirmation Is Required*
CR	CR	No	CR	>4 wks Confirmation**
CR	Non-CR/Non-PD	No	PR	
CR	Not evaluated	No	PR	
PR	Non-CR/Non-PD/not evaluated	No	PR	>4 wks Confirmation**
SD	Non-CR/Non-PD/not evaluated	No	SD	Documented at least once >4 wks from baseline**
PD	Any	Yes or No	PD	no prior SD, PR or CR
Any	PD***	Yes or No	PD	
Any	Any	Yes	PD	

* See RECIST 1.1 manuscript for further details on what is evidence of a new lesion.
 ** Only for non-randomized trials with response as primary endpoint.
 *** In exceptional circumstances, unequivocal progression in non-target lesions may be accepted as disease progression.

Note: Participants with a global deterioration of health status requiring discontinuation of treatment without objective evidence of disease progression at that time should be reported as “*symptomatic deterioration*.” Every effort should be made to document the objective progression even after discontinuation of treatment.

For Participants with Non-Measurable Disease (i.e., Non-Target Disease)

Non-Target Lesions	New Lesions	Overall Response
CR	No	CR
Non-CR/non-PD	No	Non-CR/non-PD*
Not all evaluated	No	not evaluated
Unequivocal PD	Yes or No	PD
Any	Yes	PD

* ‘Non-CR/non-PD’ is preferred over ‘stable disease’ for non-target disease since SD is increasingly used as an endpoint for assessment of efficacy in some trials so to assign this category when no lesions can be measured is not advised

11.1.5 Duration of Response

Duration of overall response: The duration of overall response is measured from the time measurement criteria are met for CR or PR (whichever is first recorded) until the first date that recurrent or progressive disease is objectively documented (taking as reference for progressive disease the smallest measurements recorded since the treatment started, or death due to any cause. Participants without events reported are censored at the last disease evaluation).

Duration of overall complete response: The duration of overall CR is measured from the time measurement criteria are first met for CR until the first date that progressive disease is objectively documented, or death due to any cause. Participants without events reported are censored at the last disease evaluation.

Duration of stable disease: Stable disease is measured from the start of the treatment until the criteria for progression are met, taking as reference the smallest measurements recorded since the treatment started, including the baseline measurements.

11.1.6 Progression-Free Survival

Overall Survival: Overall Survival (OS) is defined as the time from randomization (or registration) to death due to any cause, or censored at date last known alive.

Progression-Free Survival: Progression-Free Survival (PFS) is defined as the time from randomization (or registration) to the earlier of progression or death due to any cause. Participants alive without disease progression are censored at date of last disease evaluation.

Time to Progression: Time to Progression (TTP) is defined as the time from randomization (or registration) to progression or censored at date of last disease evaluation for those without progression reported.

11.2 Other Response Parameters

Immune related Response Criteria

New end point definitions for trials of immunologic agents have been proposed based on novel patterns of clinical activity in malignant melanoma^{98,99} and are described in detail in Appendix B. These alternative definitions allow time for immunologically mediated effectors to develop that may result in late tumor responses even after initial progression by RECIST. Also, in some patients, tumors necrosis and inflammation may increase tumor size radiographically prior to response. Changing the definitions of OR and PD may alter (increase) the number of patients achieving responses and the duration of PFS.

On a subject by subject basis, we would consider allowing study treatment to continue during initial progression up to the 12-16 weeks assessment to allow time for responses to be observed, if the patient is clinically stable, there is no deterioration in PS, and there is no need for

immediate additional treatment. While maintaining standard definitions of progression and response, we would allow new lesions and some progression beyond 20% increases in tumor measurements during the initial treatment period to allow time for responses to develop (these delayed tumor responses may be seen in 10-20% of melanoma patients who initially progress during the initial treatment cycles and evaluation). We do not have experience with response patterns with combination therapy nor in diseases other than melanoma. Please use standard response definitions as the primary end point in these studies.

Note that the proposed irRC may be incorporated as secondary end points to compare to standard criteria and evaluate alternative patterns of response in various disease setting and treatment regimens. A copy of the proposed criteria is presented in Appendix B.

Patients who demonstrate mixed responses, stable disease, or objective responses by standard RECIST following initial progression may be identified separately as “delayed SD, PR, or CR”.

Overall Risk/Benefit Assessment

The unique immune-based mechanism of action is reflected in the clinical patterns of anti-cancer activity in some patients. Immune checkpoint blockade affects tumor cells indirectly, and measurable clinical effects emerge after the immunological effects. Tumor infiltration with lymphocytes and the associated inflammation (documented by biopsy in some subjects) is likely the cornerstone of the effect of immune checkpoint inhibition and can manifest in various patterns of clinical activity leading to tumor control. In some cases, response may be preceded by an apparent increase in initial tumor volume and/or the appearance of new lesions, which may be mistaken for tumor progression on radiological evaluations. Therefore, in subjects who are not experiencing rapid clinical deterioration, confirmation of progression is recommended, at the investigator’s discretion, to better understand the prognosis as well as to avoid unnecessarily initiating potentially toxic alternative therapies in subjects who might be benefitting from treatment. Immune-related (ir) response criteria were developed based on these observations to systematically categorize novel patterns of clinical activity and are currently being prospectively evaluated in clinical studies.

In metastatic diseases, stabilization is more common than response, and in some instances is associated with slow, steady decline in tumor burden over many months, sometimes improving to partial and/or complete responses. Thus, the immune-based mechanism of action of Ipilimumab results in durable disease control, sometimes with novel patterns of response, which contribute to its improvement in OS.

The immune-based mechanism of action is also reflected in the safety profile. The most common drug-related AEs are immune-mediated, consistent with the mechanism of action of the drug and generally medically manageable with topical and/or systemic immunosuppressants. As previously discussed, the immune-mediated adverse reactions primarily involve the GI tract, skin, liver, endocrine glands, and nervous system.

The early diagnosis of immune-mediated adverse reactions is important to initiate therapy and minimize complications. Immune-mediated adverse reactions are generally manageable using

symptomatic or immunosuppressive therapy as recommended through detailed diagnosis and management guidelines, as described fully in the current IB. The management guidelines for general immune-mediated adverse reactions and Ipilimumab-related GI toxicities, hepatotoxicity, endocrinopathy, and neuropathy are provided in the appendices of the current IB.

12. DATA REPORTING / REGULATORY REQUIREMENTS

Adverse event lists, guidelines, and instructions for AE reporting can be found in Section 7.0 (Adverse Events: List and Reporting Requirements).

12.1 Data Reporting

12.1.1 Method

The Office of Data Quality (ODQ) will collect, manage, and perform quality checks on the data for this study.

12.1.2 Responsibility for Data Submission

Investigative sites within DF/HCC or DF/PCC are responsible for submitting data and/or data forms to the Office of Data Quality (ODQ) in accordance with DF/HCC policies.

12.2 Data Safety Monitoring

The DF/HCC Data and Safety Monitoring Committee (DSMC) will review and monitor toxicity and accrual data from this study. The committee is composed of medical oncologists, research nurses, pharmacists and biostatisticians with direct experience in cancer clinical research. Information that raises any questions about participant safety will be addressed with the Overall PI and study team.

The DSMC will review each protocol up to four times a year with the frequency determined by the outcome of previous reviews. Information to be provided to the committee may include: up-to-date participant accrual; current dose level information; DLT information; all grade 2 or higher unexpected adverse events that have been reported; summary of all deaths occurring within 30 days of intervention for Phase I or II protocols; for gene therapy protocols, summary of all deaths while being treated and during active follow-up; any response information; audit results, and a summary provided by the study team. Other information (e.g. scans, laboratory values) will be provided upon request.

13. STATISTICAL CONSIDERATIONS

13.1 Study Design/Endpoints

The primary goal of this Phase I trial is to assess safety of the vaccine (neoantigen peptides and poly-ICLC) and locally-delivered Ipilimumab and determine the recommended maximum tolerated dose (MTD).

Primary Endpoint: Rate of DLT(s)

Adverse events classified as dose-limiting toxicities (DLT) and the assessment time for DLTs are summarized in Section 5.5. Five patients will be treated for the initial safety evaluation (Cohort 1). We have chosen dose escalation cohorts of 5 patients, rather than a more traditional 3+3 design, because the determination of whether to treat at a different dose in this trial is made over a longer period of time due to the time required for vaccine preparation and the extended period for safety evaluation. These larger cohort sizes help us avoid having to pause and then restart enrollment to a dosing cohort several months later.

If none or only 1 patient in Cohort 1 Dose Level 1 experiences a dose limiting toxicity (DLT) during the first 7 weeks of treatment of Cohort 1, 5 patients will be treated as Cohort 2 dose Level 2. If two or more patients in Cohort 1 experience a DLT during the first 7 weeks of treatment, then 5 patients will be treated as Cohort 2 Dose Level -1.

If none or only 1 patient experiences a DLT on Cohort 2 Dose Level 2, then Dose Level 2 will be the maximum tolerated dose (MTD) and an additional 10 patients will be treated at that dose level (Cohort 3 Dose Level 2) to increase the likelihood of detecting serious toxicities, to complete biologic correlative endpoints and to gain preliminary experience with clinical tumor activity. If two or more patients in Cohort 2 Dose Level 2 experience dose limiting toxicity (DLT), then Dose Level 1 will be the MTD and an additional 10 patients will be treated in an expansion cohort (Cohort # Dose Level 1) at this dose.

If none or only 1 patient experiences a DLT on Cohort 2 Dose Level -1, then Dose Level-1 will be the maximum tolerated dose (MTD) and an additional 10 patients will be treated in an expansion cohort (Cohort 3 Dose Level -1) at that dose level. If two or more patients in Cohort 2 Dose Level -1 experience dose limiting toxicity (DLT), then the study will be stopped.

The table below shows the probability of moving to the dose expansion phase (0 or 1 patients with DLT out of 5 patients at the MTD) for various possible values of the true, but unknown, toxicity rate.

True rate of DLT (%)	Probability of Dose Expansion (%)
10	92
20	74
30	53
40	34
50	19
60	9

If the true probability of DLT is 10% or less, then the probability of proceeding to dose expansion is at least 92%. The probability of dose expansion is less than 50% if the true rate of dose-limiting toxicities is 32% or greater.

Minimum vaccination requirement to pass DLT observation period: A minimum of 2 vaccinations and absence of DLTs are required for a patient to complete the 7-week DLT observation period successfully.

Expansion Cohort: When the recommended dose has been determined, an expansion cohort of 10 patients will be treated to assess the performance of the vaccine and to gain additional information about toxicities. Because of the long lead time between patient registration and first vaccination, patients in the expansion cohort may be registered to the trial while safety in the initial cohort(s) is being assessed. Patients in the expansion cohort will not be treated until the safety evaluation of the initial cohorts is complete.

Stopping rule for Expansion Cohort: If four or more patients in the expansion cohort experience dose limiting toxicity (DLT) during the first 7 weeks of treatment, then the dose expansion cohort will be determined to have unacceptable toxicity and the study will be stopped prior to completion of enrollment of the expansion cohort. The table below summarizes the probability of observing 4 or more DLTs within the 10 patients of the expansion cohort for varying underlying rates of toxicity.

	True, but unknown, toxicity rate					
	5%	10%	20%	30%	36%	40%
Probability of observing 4 or more patients with DLT	0.001	0.013	0.121	0.350	0.513	0.618

If the true probability of DLT in the expansion cohort is higher than 35%, then the probability is at least 50% of observing 4 or more patients with DLT within the 10 patients of the expansion cohort.

Total Sample Size: The final sample size for this trial will depend upon the number of dose-escalation cohorts; however, the number of patients treated will be between 4 and 20. The minimum number of patients to be treated is based on observing DLTs after the first dose of Neoantigen Vaccine in the first two patients of Cohort 1 and similarly in Cohort 2. The maximum would occur if two dose-escalation cohorts were treated, with an additional 10 patients at the MTD.

Timelines: We expect to enroll one patient per month. We expect FPFV to occur by September 2020. LPFV is expected for July 2022 and overall duration of the study will be 4 years.

Analysis of Secondary Endpoints

Secondary endpoint in this clinical trial will: (a) assess the induction of IFN- γ T-cell response or tetramer staining to the assay peptides, and (b) to estimate rates of disease progression or recurrence (RECIST 1.1) depending on whether the patient is resected or has measurable disease. Analyses of the secondary endpoint will be based on 15 patients treated at the MTD.

The induction of IFN- γ T-cell response will be based on ELISPOT assessments taken prior to vaccine administration and at week 16. The proportion of patients who achieve more than 55 SFU/10⁶ PBMC or 3 times their baseline level will be presented with a 90% exact binomial

confidence interval. Based on a cohort of size 15, the confidence interval will be no wider than 0.46.

The proportions of patients with disease progression or recurrence, according to melanoma stage, will be presented with 90% exact binomial confidence intervals.

Analysis of Correlative Endpoints

Longitudinal analyses of PBMC immune response kinetics to the peptide pool and to individual epitopes will be presented graphically and descriptively at each time point. Changes in the magnitude of the response relative to pre-treatment at several different time points after vaccination will be summarized descriptively. Changes in response between pre-treatment and 16 weeks post-vaccination, which is the time of the primary immunologic endpoint, will be assessed using the Wilcoxon signed-rank test.

Immune studies of T cell subpopulations (CD4⁺, CD8⁺, central/effector memory cells, Th1/Th2 cells, T-reg, etc.), myeloid-derived suppressor cells (MDSC), CTL response, and T cell activation status will be summarized using descriptive statistics.

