If zero or 1 patient in Cohort 1 experienced a dose limiting toxicity (DLT) during the first 7 weeks of treatment, 5 patients would be treated as Cohort 2 (Ipilimumab 5 mg per injection site). If two or more patients in Cohort 1 experienced a DLT during the first 7 weeks of treatment, then 5 patients would be treated at Cohort -1 (Ipilimumab 1.25 mg per injection site). If none or 1 patient experienced a DLT on Cohort 2, then Ipilimumab at 5 mg per injection site would be the maximum tolerated dose (MTD) and an additional 10 patients will be treated at that dose level to increase the likelihood of detecting serious

toxicities, to complete biologic correlative endpoints, and to gain preliminary experience with clinical tumor activity. If two or more patients in Cohort 2 experienced DLT, then Dose Level 1 would be the MTD and an additional 10 patients would be treated in an expansion cohort at this dose.

If no or only 1 patient experienced a DLT on Cohort -1, then Ipilimumab 1.25 mg per injection site would be the MTD and an additional 10 patients would be treated in an expansion cohort at that dose level. If two or more patients in Cohort -1 experienced DLT, then the study will be stopped and no MTD would be declared.

The table below shows the probability of moving to the dose expansion phase (0 or 1 patients with DLT out of 5 patients at the MTD) for various possible values of the true, but unknown, toxicity rate.

True rate of DLT (%)	Probability of Dose Expansion (%)
10	92
20	74
30	53
40	34
50	19
60	9

If the true probability of DLT is 10% or less, then the probability of proceeding to dose expansion is at least 92%. The probability of dose expansion is less than 50% if the true rate of dose-limiting toxicities is 32% or greater.

**Minimum vaccination requirement to pass DLT observation period:** A minimum of 2 vaccinations and absence of DLTs are required for a patient to complete the 7-week DLT observation period successfully.

**Modified Design:** Due to slow accrual in this trial, enrollment to the expansion cohort did not begin and trial accrual was stopped at the end of the dose escalation phase, at the time the MTD was determined.

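### The probability-of-dose-expansion column gives the chance that one five-patient cohort clears; with a 32% DLT rate at every dose level the rules lead to expansion about 74% of the time, not under 50%

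*Protocol*

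**What the plan says.** Protocol 13.1 sets the escalation rules, and Protocol 5.4.1 and the SAP's Design section give the same ones. Cohort 1 is five patients at Dose Level 1.

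- With 0 or 1 DLT, "5 patients will be treated as Cohort 2 dose Level 2". If that cohort also has 0 or 1 DLT, Level 2 is the MTD and ten more patients are treated there. If it does not: "If two or more patients in Cohort 2 Dose Level 2 experience dose limiting toxicity (DLT), then Dose Level 1 will be the MTD", again with ten more patients.
- With two or more DLTs in Cohort 1, five patients are treated at Dose Level -1. If 0 or 1 has a DLT, Level -1 is the MTD and is expanded. Otherwise: "If two or more patients in Cohort 2 Dose Level -1 experience dose limiting toxicity (DLT), then the study will be stopped". The SAP states the same end point: "If two or more patients in Cohort -1 experienced DLT, then the study will be stopped and no MTD would be declared".

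A table follows. It is introduced as the probability of entering the expansion phase, with a parenthesis describing the event as "0 or 1 patients with DLT out of 5 patients at the MTD". It lists one true DLT rate per row (10 to 60%) and gives 92, 74, 53, 34, 19 and 9% under a column headed as the probability of dose expansion. The text then concludes: "The probability of dose expansion is less than 50% if the true rate of dose-limiting toxicities is 32% or greater". The SAP, dated November 20, 2023, repeats both the table and the sentence.

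**The concern.** The table is the only operating characteristic the plan states for its escalation rules, in a trial whose primary endpoint is the DLT rate. A reader takes from it that, at a DLT rate of 32% or more, the trial is more likely than not to end without an expansion cohort. The rules allow several routes to expansion, so a figure that describes one cohort cannot also describe the whole design. If the column is mislabelled, the plan claims more protection during escalation than its rules provide. The separate rule for the expansion cohort (four or more DLTs among ten) helps only once expansion has started.

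**Working it through.** **Inputs** (Protocol 13.1; same in the SAP): cohort size 5; a cohort clears with 0 or 1 DLT; the branching rules above; one DLT rate per table row.

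**Step 1: reproduce the plan's column.** For one cohort with DLT rate p,

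q(p) = (1 - p)⁵ + 5p(1 - p)⁴.

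This gives 0.9185, 0.7373, 0.5282, 0.3370, 0.1875 and 0.0870 at 10, 20, 30, 40, 50 and 60%. Rounded, these are all six tabulated values. Also q(0.32) = 0.4875, and q crosses 0.5 at p = 31.4%. The 32% sentence is therefore a statement about one cohort.

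**Step 2: follow the rules to their end.**

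| Level 1 | Next cohort | Outcome |
|---|---|---|
| clears | Level 2 clears | expansion at Level 2 |
| clears | Level 2 fails | expansion at Level 1 |
| fails | Level -1 clears | expansion at Level -1 |
| fails | Level -1 fails | study stops |

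Hence P(expansion) = q(L1) + [1 - q(L1)] × q(L-1). The Level 2 rate decides where expansion happens, not whether it happens.

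**Step 3: same rate at every level.** The formula becomes 1 - (1 - q)². At 32%: 0.4875 + 0.5125 × 0.4875 = 0.737. The four outcomes, in table order, have probabilities:

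- q² = 0.238
- q(1 - q) = 0.250
- (1 - q)q = 0.250
- (1 - q)² = 0.263

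Simulating the rules at 32% (300,000 runs) gave 0.737.

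| True DLT rate | Stated (%) | Whole design (%) |
|---|---|---|
| 10% | 92 | 99 |
| 20% | 74 | 93 |
| 30% | 53 | 78 |
| 32% | below 50 | 74 |
| 40% | 34 | 56 |
| 50% | 19 | 34 |
| 60% | 9 | 17 |

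The whole-design probability equals 50% when (1 - q)² = 0.5, which is at p = 42.6%.

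**Step 4: unequal rates.** The documents give no dose-specific rates, so these are illustrative assumptions for Levels -1/1/2.

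- 20/32/45%: 0.4875 + 0.5125 × 0.7373 = 0.865
- 32/40/50%: 0.3370 + 0.6630 × 0.4875 = 0.660
- 40/50/60%: 0.1875 + 0.8125 × 0.3370 = 0.461

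**Step 5: allow for the expansion stopping rule.** At a 40% DLT rate the plan gives 0.618 for four or more DLTs among ten. At a common 40%, the probability of reaching expansion and not meeting that rule is 0.560 × 0.382 = 0.214. It would be 0.337 × 0.382 = 0.129 if the tabulated 34% were the expansion probability.

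**The case against.** The strongest defence is that the event is disclosed. The parenthesis "0 or 1 patients with DLT out of 5 patients at the MTD" describes one cohort, and every entry is exact for that event. There is also a coherent narrower reading: q at the Level 1 rate is the probability of expanding at the starting dose or higher (48.8% at 32%). It is fair to say that no number was miscalculated and that the fault lies in the label and the interpretation.

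The defence does not save the 32% sentence. That sentence carries no qualifier, and the MTD is an output of the rules. Every route to expansion ends with a declared MTD at which 0 or 1 of 5 patients had a DLT, so the parenthesis excludes none of them. Nor does the column give the probability of expansion at Level 2, which is q(L1) × q(L2), or 24% at a common 32%.

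A second objection is that the documents never say one rate applies at all three levels, so the 74% rests on an assumption. That is right, and the assumption must be stated. The table, however, offers only one rate per row. If 32% is the Level 1 rate and Level -1 is no more toxic, 74% is a lower bound. The 40/50/60% case does fall below 50%, so the figure can move either way.

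Finally, a reader has the full rules just above the table, no decision, endpoint analysis or sample size uses it, and the SAP's Modified Design paragraph says "enrollment to the expansion cohort did not begin and trial accrual was stopped at the end of the dose escalation phase". These points limit the consequences and stand. They do not make the sentence correct, and the current SAP still carries it.

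**Conclusion.** The concern holds. The column and the 32% sentence describe clearance of a single five-patient cohort but are presented as the probability of dose expansion. With the same DLT rate at every level, expansion at 32% has probability 74% and stopping 26%, and the probability drops below 50% only above about 43%. Between 32% and about 43% the stated conclusion is therefore wrong in direction under that assumption. The companion sentence, at least 92% when the rate is 10% or less, remains true (99% at a common 10%). The error affects the design properties stated in the protocol and the SAP, and in any report that repeats them. It changes no decision rule and no estimate, and no patient was enrolled to expansion.

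**What to change.** In Protocol 13.1 and the SAP's Design section:

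1. Relabel the existing column as the probability that a single five-patient cohort clears (0 or 1 DLT).
2. Add a column for the probability of dose expansion assuming the same DLT rate at every dose level: 99, 93, 78, 56, 34 and 17% for 10 to 60%.
3. Replace the 32% sentence with: Assuming the same DLT rate at every dose level, the probability of expansion is below 50% only if that rate exceeds about 43%.
4. Preferably add one or two labelled illustrations with unequal rates at Levels -1/1/2, such as 20/32/45% (87%) and 40/50/60% (46%), to show that the figure moves in both directions.

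Items 1 to 3 correct the error, and item 4 helps the reader. The cost is a label, a column, a sentence and an optional line in each of two documents. Decision rules and sample size stay as they are. The one drawback is that the stated operating characteristic becomes less favourable.
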